### **8.3.2.8. Injection-Site Reactions**

Symptoms of a local injection-site reaction may include erythema, induration, pain, pruritus, and edema. If an injection site event is reported, the AE will be recorded, and additional data will be provided to the sponsor in the eCRF.

Injection site reactions will be collected on the eCRF separate from the hypersensitivity reaction eCRF. At the time of AE occurrence, samples will be collected for measurement of tirzepatide antidrug antibodies (ADA) and tirzepatide concentration.

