## **8.9. Immunogenicity Assessments**

Where local regulations and ERBs allow, blood samples for immunogenicity testing will be collected to determine antibody production against tirzepatide as specified in the SoA (Section 1.3).

For immunogenicity testing, venous blood samples will be collected from each participant according to the SoA (Section 1.3) to determine antibody production against tirzepatide. To interpret the results of immunogenicity, a PK sample will be collected at the same time points as the immunogenicity sample. All samples for immunogenicity should be taken predose when applicable and possible.

In the event of systemic drug hypersensitivity reactions (immediate or nonimmediate), additional unscheduled samples will be collected as detailed in Section 8.3.2.7 (Hypersensitivity Reactions).

Instructions for the collection and handling of blood samples will be provided by the sponsor. The actual date and time (24-hour clock time) of each sampling will be recorded. Samples collected at Visit 801 will assess immunogenicity at washout of tirzepatide (5 half-lives post end of treatment).

Immunogenicity will be assessed by a validated assay designed to detect ADAs in the presence of tirzepatide at a laboratory approved by the sponsor. Antibodies may be further characterized for their ability to neutralize the activity of tirzepatide on GIP and GLP-1 receptors. Positive tirzepatide ADA samples will be tested for cross-reactivity with native GIP and GLP-1, and, if positive, may then be tested for neutralizing antibodies against native GIP and/or GLP-1. In vivo laboratory indicators for effect on weight loss and PK will be utilized to detect potential neutralizing effect of ADA against tirzepatide.

Treatment-emergent ADAs are defined in Section 9.4.6.

Samples will be retained for a maximum of 15 years after the last participant visit, or for a shorter period if local regulations and ERBs allow, at a facility selected by the sponsor. The duration allows the sponsor to respond to future regulatory requests related to tirzepatide. Any samples remaining after 15 years will be destroyed.

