Immunogenicity Postbaseline Period Observations

Postbaseline period observations for each participant include all observations after the first administration of study drug. There are 2 different periods:

- The planned treatment period is defined as from the first dose of treatment to end of the treatment period.
- The entire postbaseline period is defined as from the first dose of treatment to the end of the safety follow-up visit or the date of study withdrawal.

4.6.5.5.3. *Definitions of Participant ADA Status*

Participants Evaluable for Treatment-Emergent ADA (TE ADA)

A participant is evaluable for TE ADA if the participant has a nonmissing baseline ADA result and at least 1 nonmissing postbaseline ADA result.

TE-ADA-Unevaluable Participants

A TE ADA-unevaluable participant is any participant who does not meet the evaluable criteria.

Baseline ADA Present (preexisting antibody)

Anti-drug antibodies are detected in a sample collected up to the first dose date and time.

Baseline ADA Not Present

Anti-drug antibodies are not detected, and the corresponding PK concentrations are missing or are below the drug tolerance limit in a sample collected up to the first dose date and time.

Treatment-Emergent ADA-Positive (TE ADA+) Participants

A participant who is evaluable for TE ADA is TE ADA+ if either of the following holds:

- The participant has baseline status of ADA Not Present and at least 1 postbaseline status of ADA Present with titer $\geq 2 \times$ the minimum required dilution (MRD) of the ADA assay.
- The participant has baseline and postbaseline status of ADA Present, with the postbaseline titer being 2 dilutions (4-fold) greater than the baseline titer. That is, the participant has a baseline status of ADA Present, with a titer of 1:baseline, and at least 1 postbaseline status of ADA Present, with a titer of 1:postbaseline, with postbaseline divided by baseline ≥ 4 .

As shown in [Figure GPHM.4.1](#), a titer is expected when an ADA assay result is Detected. On occasion, the corresponding assay cannot be performed, in which case a titer value will be imputed for the purpose of TE ADA determination. A baseline sample with detected ADA and no titer is imputed to be the MRD (1:10), and a postbaseline sample with ADA detected and no titer is imputed to be 1 dilution above the MRD (1:20).

Treatment-Emergent ADA-Inconclusive Participants

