A participant who is evaluable for TE ADA is TE ADA Inconclusive if $\geq 20\%$ of the participant's postbaseline samples are ADA Inconclusive and all remaining postbaseline samples are ADA Not Present.

Treatment-Emergent ADA-Negative (TE ADA-) Participants

A participant who is evaluable for TE ADA is TE ADA- when the participant is not TE ADA+ and the participant is not TE ADA Inconclusive.

For each NAb assay, the following are defined:

- NAb-positive (NAb+) participant - A participant who is TE ADA+ and has an NAb positive sample in the postbaseline period.
- NAb-Inconclusive participant - A participant who is TE ADA+, is not NAb+, and all samples that have TE ADA+ titer have an NAb Inconclusive sample result.
- NAb-negative (NAb-) participant - A participant is NAb- when the participant is neither NAb+ nor NAb Inconclusive.

Unless specified otherwise, the above-mentioned definitions of NAb are applicable to all NAb analyses, including cross-reactive NAb analyses and cross-reactive antibodies.

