4.6.5.5.4. Analyses to be Performed

The count and proportion of participants who are TE ADA+ will be tabulated by treatment group, where proportions are relative to the number of participants who are TE ADA evaluable, as defined above. The tabulation will include the number and proportion of participants with

ADA Present at baseline and the number and proportion of TE-ADA+ participants exhibiting each type of cross-reactive antibody and NAb. This analysis will be performed for the following periods:

- the planned treatment period, and
- the entire postbaseline period, including safety follow-up.

The *in silico* classification for cross-reactive NAb will be summarized.

A summary will be provided of the count and percentage of tirzepatide-treated participants experiencing a specific TEAE (see [Table GPHM.4.10](#)) by participant TE-ADA status (TE ADA+, TE ADA-, or TE ADA Inconclusive).

Table GPHM.4.10. Adverse Events for Analysis with Immunogenicity Results

TEAE Category	Criteria
Hypersensitivity reactions	Anaphylaxis SMQ (narrow or algorithm)
	Hypersensitivity SMQ (narrow)
	Angioedema SMQ (narrow)
	Severe Cutaneous Adverse Reaction SMQ (narrow)
	Vasculitis SMQ (narrow)
Injection site reactions	Injection site reaction HLT
	Infusion site reaction HLT
	Administration site reaction HLT

Abbreviations: HLT = High-Level Term; MedDRA = Medical Dictionary for Regulatory Activities; SMQ = Standardized MedDRA Query; TEAE = treatment-emergent adverse event.

A listing will be provided for all participants who had ADA Present at any time (including baseline) or had any specific TEAE (see [Table GPHM.4.10](#)). This listing includes a time course of ADA (clinical interpretation result plus flags for samples meeting TE ADA+ criteria and for samples with cross-reactive antibodies and NAb present) along with the TEAE.

Cases of TE ADA that are associated with AEs of either severe/serious hypersensitivity or severe/serious injection site reaction (ISR) will be classified as AESI.

Additional immunogenicity analyses, as determined later, may be presented. The relationship between antibody titers, the PK parameters, and pharmacodynamic (PD) response to tirzepatide may also be assessed.

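### The planned table of injection-site and hypersensitivity reactions by treatment-emergent ADA status counts ADA samples that were drawn because a reaction occurred, which biases it toward an association

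*SAP*

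**What the plan says.** **Which samples count.** SAP section 4.6.5.5.2: "Postbaseline period observations for each participant include all observations after the first administration of study drug". Section 4.6.5.5.3 makes a participant TE ADA+ on a single sample. Without ADA at baseline, the rule is "at least 1 postbaseline status of ADA Present with titer" at or above twice the minimum required dilution. With ADA at baseline, it is "at least 1 postbaseline status of ADA Present, with a titer of 1:postbaseline, with postbaseline divided by baseline" at least 4. A participant is TE ADA Inconclusive if at least 20% of "postbaseline samples are ADA Inconclusive and all remaining postbaseline samples are ADA Not Present".

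**Which samples a reaction triggers.** For injection-site reactions, protocol section 8.3.2.8 says: "At the time of AE occurrence, samples will be collected for measurement of tirzepatide antidrug antibodies (ADA) and tirzepatide concentration". For hypersensitivity, section 8.9 says: "In the event of systemic drug hypersensitivity reactions (immediate or nonimmediate), additional unscheduled samples will be collected", and refers to section 8.3.2.7. That section asks for samples in generalized urticaria or anaphylaxis. Appendix 3 (section 10.3) adds a follow-up sample at the next scheduled visit or after 4 weeks, whichever is later.

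**How status is used.** SAP section 4.6.5.5.4: "A summary will be provided of the count and percentage of tirzepatide-treated participants experiencing a specific TEAE", split by TE ADA+, TE ADA- and TE ADA Inconclusive. The events are those in Table GPHM.4.10: hypersensitivity (five SMQs) and injection-site reactions (three High-Level Terms). The same section classifies TE ADA associated with a severe or serious reaction of either kind as an AESI. It also plans a listing of the ADA time course beside the event.

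**The concern.** In this table ADA status is the exposure and the reaction is the outcome, yet the outcome itself prompts further measurement of the exposure. A participant with an injection-site reaction has more chances to show one qualifying sample than a participant without one. An added sample can create TE ADA+ status but can never remove it.

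Sections 4.6.5.5.1 to 4.6.5.5.4 contain nothing that limits status to scheduled or pre-event samples. Elsewhere the SAP does make that distinction. Change-from-baseline analyses of laboratory values, vital signs and ECGs use scheduled visits only (Table GPHM.4.1, row 1.3), and mean-change analyses of vital signs and ECGs use planned measurements only (sections 4.6.3.4 and 4.6.3.5).

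At stake is how a safety table will be read. It is the cross-tabulation the SAP commits to on whether antibodies go with these reactions, and its percentages will be taken as evidence on that question.

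**Working it through.** The documents state no figure on this point, so there is none to reproduce. The calculations below assume no true association and ask what the table would show.

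**Inputs**
- Scheduled postbaseline ADA samples for a completer: 5 (Weeks 4, 12, 24, 72 and Visit 801). The protocol Schedule of Activities also has one at ED. This is my reading of a table that did not survive extraction intact.
- Extra samples k: 1 for one injection-site reaction, or 2 for two such reactions or a sampled systemic reaction with its follow-up.
- Tirzepatide arm: 300 (protocol section 9.2).
- ADA rate, reaction rate and persistence: assumed throughout.

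**Independent samples (upper end).** Let b be the TE ADA+ rate from the 5 scheduled samples. The per-sample rate is p = 1 - (1 - b)^(1/5). With k extra samples, q = 1 - (1 - p)^(5+k) = 1 - (1 - b)^((5+k)/5). The apparent odds ratio is [q/(1 - q)] / [b/(1 - b)].

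For b = 0.50:
- k = 1: q = 1 - 0.5^1.2 = 0.565, odds ratio 1.30
- k = 2: q = 1 - 0.5^1.4 = 0.621, odds ratio 1.64

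For b from 0.10 to 0.70:

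| b | k = 1 | k = 2 |
|---|---|---|
| 0.10 | 1.21 | 1.43 |
| 0.30 | 1.25 | 1.51 |
| 0.50 | 1.30 | 1.64 |
| 0.70 | 1.39 | 1.88 |

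To see this in the table's own terms, take b = 0.50 and a 10% reaction rate, so 30 of 300 participants react.
- k = 1: reactions in 0.1 × 0.565 / (0.1 × 0.565 + 0.9 × 0.5) = 11.2% of TE ADA+ against 8.8% of TE ADA-
- k = 2: 12.1% against 7.8%

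In people, one extra sample moves 30 × (0.565 - 0.500), about 2 participants, into TE ADA+. Two extra samples move 30 × (0.621 - 0.500), about 4.

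**Antibodies that persist for a time (simulation, 400,000 participants).** Assume 30% or 60% develop ADA at a uniform time over Weeks 0 to 72. Duration is exponential with mean 8 to 52 weeks, or permanent. The reaction time is independent of ADA. One sample is drawn at the event, or two with the second 4 weeks later.

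| Setting | 1 extra | 2 extra |
|---|---|---|
| Reactions over Weeks 0-72, time-limited ADA | 1.08-1.22 | 1.10-1.34 |
| Reactions in Weeks 0-24, time-limited ADA | 1.01-1.06 | 1.02-1.12 |
| Permanent ADA | 1.00 | 1.00 |

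With permanent antibodies, Week 72 and Visit 801 catch every case, so extra samples add nothing.

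**The other columns.** The Inconclusive rule is a percentage of samples, so it also depends on how many are drawn. One Inconclusive sample among 5 is 20% (TE ADA Inconclusive if the rest are Not Present). Among 6 it is 16.7% (TE ADA-).

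**Status from scheduled samples only.** With no event-driven samples and equal scheduled follow-up, the sampling-driven odds ratio is 1.00 by construction in both models.

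**The case against.** The strongest case on the other side has five parts.

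- *The direction is not assured in practice.* The calculation gives participants with a reaction all 5 scheduled samples plus extras. Protocol section 7.1 has participants with a drug-related systemic reaction stop study drug permanently. They are asked to stay but may decline visits. With b = 0.50 and only 4 samples in total against 5 for others, q = 1 - 0.5^0.8 = 0.426 and the odds ratio is 0.74. This stands: the bias is toward an association only with other things equal.
- *The hypersensitivity row is only partly exposed.* Section 8.9 is worded broadly but defers to section 8.3.2.7, which names generalized urticaria and anaphylaxis. The Appendix 3 table says the ADA test may be obtained. Table GPHM.4.10 counts five SMQs, so many tabulated events need trigger no sample. The follow-up may also coincide with a scheduled sample. This stands.
- *Timing.* Routine samples are taken before dosing, whereas a reaction sample may follow a dose. Drug interference may turn a Not Detected result into Inconclusive. That would weaken the bias, but cannot undo a positive from another sample.
- *The table is descriptive.* Only counts and percentages are planned, with no test by ADA status. This stands and limits the consequence.
- *The listing covers it.* A reader might infer that a real link could not be told apart from extra sampling. The documents do not support that: the listing flags the samples that meet TE ADA+ criteria beside the event, so participants positive only on an event-driven sample can be found. What remains is that the listing does not correct the tabulated percentages.

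**Conclusion.** TE ADA status is partly ascertained because of the outcome it is tabulated against. Other things equal, the TE ADA+ column is biased toward an association, most clearly for injection-site reactions and only partly for hypersensitivity.

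The mechanism is documented, but its size is not. It ranges from nil (permanent antibodies), through odds ratios of about 1.0 to 1.3 (time-limited antibodies), to about 1.2 to 1.9 (one or two extra samples, full independence between a person's samples). The last is an upper end for that number of samples; repeated reactions would add more. Lost scheduled visits could cancel or reverse it.

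A reader might infer that the table will show an association even when there is none. The documents do not support that: the bias can be zero, and they give no ADA rate, reaction rate or persistence from which to fix its size. Nor does any efficacy or confirmatory conclusion depend on it. The point is a cheap improvement to a descriptive safety table.

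**What to change.** In SAP section 4.6.5.5.4, for the Table GPHM.4.10 cross-tabulation:

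1. Derive TE ADA+, TE ADA- and TE ADA Inconclusive from protocol-scheduled samples: Weeks 4, 12, 24, 72, ED and Visit 801. ED belongs on the list because participants who stop because of a reaction may have few later samples.
2. Show the all-samples version beside it.
3. Flag event-driven samples in the listing, including an ED visit that is itself the reaction visit. Such a sample is scheduled in name but prompted by the event, so a little of the bias can remain.
4. Keep all samples for the AESI classification in the same section, and say so.

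The cost is a few lines of SAP text, one derivation flag and one extra display, with no new data. The small downside is that a transient response seen only at the event appears only in the all-samples version and the listing. Unequal follow-up after stopping drug is not cured by this change, so the number of scheduled samples per participant should be borne in mind when reading either version.

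### One low-titer ADA Present sample blocks the TE ADA Inconclusive class, so participants with mostly unreadable samples are counted as TE ADA- in the TEAE-by-antibody-status summary

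*SAP*

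**What the plan says.** SAP 4.6.5.5.1 (Tables GPHM.4.7 and GPHM.4.8) classifies single samples. Any Detected result is ADA Present, with no minimum titer. A Not Detected result is ADA Not Present if drug concentration is below the assay's tolerance, and ADA Inconclusive if it is at or above it.

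SAP 4.6.5.5.3 then classifies participants who have a baseline and at least one postbaseline result:

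- **TE ADA+**, by either of two routes. With baseline Not Present, the participant needs "at least 1 postbaseline status of ADA Present with titer" at least twice the minimum required dilution (MRD). With baseline Present, the participant needs a later Present sample "with the postbaseline titer being 2 dilutions (4-fold) greater than the baseline titer".
- **TE ADA Inconclusive**: at least 20% of the "postbaseline samples are ADA Inconclusive and all remaining postbaseline samples are ADA Not Present".
- **TE ADA-**: the residual. An evaluable participant "is TE ADA- when the participant is not TE ADA+ and the participant is not TE ADA Inconclusive".

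SAP 4.6.5.5.4 uses this three-way status in a summary of counts and percentages of hypersensitivity and injection-site TEAEs among tirzepatide-treated participants. The same section tabulates the TE ADA+ proportion over all evaluable participants, and lists everyone with ADA Present at any time together with their sample history and events.

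**The concern.** ADA Present and treatment-emergent have different thresholds, and the Inconclusive rule takes no account of the band between them. A Present sample in that band does not make the participant TE ADA+, but it breaks the condition that every other sample be Not Present. The residual rule then returns TE ADA-, however many of the other samples were unreadable.

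This runs the wrong way. Replacing an unreadable sample by a detected antibody moves the participant from Inconclusive to negative, although the remaining unreadable samples are the ones where a rise in titer could be masked. A plausible route is preexisting antibody that persists without boosting, with on-drug samples affected by drug interference and a readable positive at Visit 801, which Protocol 8.9 describes as a washout sample.

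At stake is the meaning of the TE ADA- row in the TEAE summary. It would hold some participants whose treatment-emergent status could not be read, and the Inconclusive row would be too small.

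**Working it through.** The plan states no figure for this point, so there is none to reproduce. The check applies the definitions to sample patterns.

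**Inputs**
- MRD 1:10 (Protocol 9.4.6; SAP 4.6.5.5.3). The TE ADA+ cut-off with baseline Not Present is therefore 2 × 10, a titer of 1:20. This agrees with the SAP's own imputed value of 1:20 for one dilution above the MRD.
- TE ADA+ cut-off with baseline Present: postbaseline titer ÷ baseline titer ≥ 4.
- Imputation when ADA is detected without a titer: 1:10 at baseline, 1:20 postbaseline (SAP 4.6.5.5.3).
- Scheduled postbaseline samples for a completer: Weeks 4, 12, 24, 72 and Visit 801, so five, of which four fall in the treatment period (Protocol 1.3, immunogenicity row).

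**Classification under the current rule and with the clause on remaining samples deleted**

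| Baseline | Postbaseline samples | Inconclusive share | Current | Clause deleted |
|---|---|---|---|---|
| Not Present | 5 Inconclusive | 5/5 = 100% | Inconclusive | Inconclusive |
| Not Present | 4 Inconclusive, 1 Present at 1:10 | 4/5 = 80% | TE ADA- | Inconclusive |
| 1:20 | 4 Inconclusive, 1 Present at 1:40 (2-fold) | 80% | TE ADA- | Inconclusive |
| Detected, no titer (1:10) | 4 Inconclusive, 1 Present, no titer (1:20, 2-fold) | 80% | TE ADA- | Inconclusive |
| Not Present | 3 Inconclusive, 1 Present at 1:10 (treatment period only) | 3/4 = 75% | TE ADA- | Inconclusive |
| Not Present | 4 Inconclusive, 1 Present at 1:20 | 80% | TE ADA+ | TE ADA+ |
| 1:20 | 4 Inconclusive, 1 Present at 1:80 (4-fold) | 80% | TE ADA+ | TE ADA+ |
| Not Present | 1 Inconclusive, 4 Not Present | 1/5 = 20% | Inconclusive | Inconclusive |
| Not Present | 5 Not Present | 0% | TE ADA- | TE ADA- |

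**How many patterns change.** Take baseline Not Present and let each sample be Inconclusive, Not Present, or Present at 1:10. With five samples there are 21 mixes. Those that change have at least one Inconclusive (1/5 already reaches 20%) and at least one Present: 4 + 3 + 2 + 1 = 10. With four samples, 3 + 2 + 1 = 6 of 15 change. These count patterns, not participants. TE ADA+ is decided before the Inconclusive share is considered, so no TE ADA+ participant changes class.

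**How many participants.** The documents give no rate of preexisting or low-titer ADA, no rate of Inconclusive samples and no drug-tolerance value. Suppose 3% to 10% of 300 tirzepatide participants have such antibody, each of the four on-drug samples is Inconclusive with probability r, and Visit 801 is readable. The expected number with at least one Inconclusive sample is 300 × prevalence × [1 − (1 − r)^4]:
- 3%, r = 0.10: 9 × 0.344 = 3.1
- 10%, r = 0.50: 30 × 0.9375 = 28.1

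Each figure is an upper bound under its own assumptions, because reclassification also needs a postbaseline Present sample and no TE ADA+ result. If each readable sample is Present with probability q, the bracket becomes the sum over k = 1 to 4 of C(4,k) r^k (1 − r)^(4−k) [1 − (1 − q)^(5−k)]. At r = 0.50 and 10% prevalence this gives 30 × 0.583 = 17.5 for q = 0.3 and 30 × 0.241 = 7.2 for q = 0.1. If drug rarely interferes with the assay, the number could be close to zero.

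**The case against.** The case against giving this weight is strong on consequence. The summary concerned shows counts and percentages, with no test planned, and the SAP does not call TE ADA- a comparator. The headline immunogenicity result, the TE ADA+ proportion, uses all evaluable participants as its denominator and is untouched. The rule that makes some TE ADA cases adverse events of special interest is untouched too. Every affected participant has an ADA Present sample and so appears in the listing, sample by sample. With baseline Not Present, a detected sample lacking a titer is imputed at 1:20 and becomes TE ADA+, so on that route only a measured titer below 1:20 causes the problem. All of this stands and limits the size of the point.

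Some stronger readings also fail:
- A reader might infer that the rule contradicts the SAP's treatment of Not Detected results at high drug concentration. That treatment governs how one sample is read and sets no rule for mixed results in a participant.
- A reader might infer that the clause is what puts antibody carriers into TE ADA-. A participant with readable, persistent, non-boosted antibody belongs there, because the class means not shown to be treatment-emergent. It does not mean antibody-free.
- A reader might infer that one Inconclusive plus four Not Present should not be Inconclusive. That follows from the 20% threshold, which is not at issue here.
- A reader might infer that the neutralizing-antibody Inconclusive rule needs the same change. It applies only to samples at TE ADA+ titer within TE ADA+ participants, and nothing in the documents supports carrying a 20% threshold over to that denominator.

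None of this removes the logical gap. No other section of either document closes it, and no rationale for the clause is given.

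**Conclusion.** The point holds as a definitional error of limited reach. As written, the rule assigns TE ADA- to participants with up to four of five samples unreadable, solely because the remaining sample contains antibody below the treatment-emergent cut-off. The conclusion rests only on the SAP's definitions and the five scheduled samples, not on any assumed rate.

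The effect is confined to the split between TE ADA- and TE ADA Inconclusive in the one descriptive TEAE summary. The number of participants cannot be estimated from the documents. The range of about 3 to 28 is at most an upper bound under assumed rates and should not be read as a forecast. The correction is worth making because it is cheap and leaves every TE ADA+ participant where they are.

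**What to change.** In SAP 4.6.5.5.3, define TE ADA Inconclusive as: evaluable for TE ADA, not TE ADA+, and at least 20% of postbaseline samples ADA Inconclusive. Delete the clause on remaining samples. TE ADA- can stay as the residual class. If the clause was deliberate, state the reason in the SAP instead.

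The cost is one sentence and one programming condition. The downside is that a few more participants are shown as Inconclusive, including some who are mostly readable: for example, one Inconclusive sample plus four non-emergent positives would move from TE ADA- to Inconclusive with 80% of samples readable. No change to the neutralizing-antibody definitions is proposed.
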